3.0 PATIENT ELIGIBILITY: SELECTION AND ENROLLMENT OF PARTICIPANTS

Subjects must meet all of the inclusion and exclusion criteria to be registered to the study. Study treatment may not begin until a subject is registered.

3.1 Inclusion Criteria

- 3.1.1 History of low back pain for a minimum of 6 months with or without signs and symptoms of radiculopathy
- 3.1.2 Male or female, between the ages of 18 and 75 years, with no racial/ethnic restrictions
- 3.1.3 Must have a Visual Analog Scale (VAS) pain score ≥ 5 mm (of 10 mm maximum) at the screening visit (for which 0mm = no pain, and 10 mm = worst pain imaginable);
- 3.1.4 Must be able to read and speak English and be willing to read and understand instructions as well as questionnaires;
- 3.1.5 Must be in generally stable health;
- 3.1.6 Must sign an informed consent document after a complete explanation of the study documenting that they understand the purpose of the study, procedures to be undertaken, possible benefits, potential risks, and are willing to participate
- 3.1.7 Must have, on average, \geq to 5/10 units of pain over the course of a two-week period prior to visit 1; rounding up from 4.5/10 is permissible.
- 3.1.8 Must be willing to complete daily smart phone/computer app ratings.

3.2 Exclusion Criteria

- 3.2.1 Low back pain associated with any systemic signs or symptoms, e.g., fever, chills;
- 3.2.2 Evidence of rheumatoid arthritis, ankylosing spondylitis, acute vertebral fractures, fibromyalgia, history of tumor in the back;
- 3.2.3 Other comorbid chronic pain or neurological conditions;
- 3.2.4 Involvement in litigation regarding their back pain or having a disability claim or receiving workman's compensation or seeking either as a result of their low back pain;
- 3.2.5 Diagnosis of current depression or psychiatric disorder requiring treatment, or such a diagnosis in the previous 6 months;
- 3.2.6 Beck Depression Inventory (BDI) Ia score ≥ 19 for two consecutive completions; if the first score meets this criteria, the participant must be re-tested before his/her next visit, but if the second score does not meet this criteria, the participant will be included and followed closely throughout the study
- 3.2.7 Use of therapeutic doses of antidepressant medications (i.e., tricyclic depressants, SSRIs, SNRIs; low doses used for sleep may be allowed);
- 3.2.8 Significant other medical disease such as unstable diabetes mellitus, congestive heart failure, coronary or peripheral vascular disease, chronic obstructive lung disease, or malignancy;
- 3.2.9 History of gastrointestinal ulcer during the past year;
- 3.2.10 History of myocardial infarction in the past year;
- 3.2.11 Uncontrolled hypertension;
- 3.2.12 Renal insufficiency;
- 3.2.13 Allergic to, or non-tolerant of, NSAIDs;
- 3.2.14 History of aspirin-sensitive asthma;
- 3.2.15 Current use of recreational drugs or history of alcohol or drug abuse;
- 3.2.16 Any change in medication for back pain in the last 30 days only applicable for visit 1
- 3.2.17 High dose opioid prophylaxis, as defined as > 50 mg morphine equivalent/day;
- 3.2.18 Any medical condition that in the investigator's judgment may prevent the individual from completing the study or put the individual at undue risk;
- 3.2.19 In the judgment of the investigator, unable or unwilling to follow protocol and instructions;
- 3.2.20 Evidence of poor treatment compliance, in the judgment of the investigator;
- 3.2.21 Intra-axial implants (e.g. spinal cord stimulators or pumps);
- 3.2.22 All exclusion criteria for MR safety: any metallic implants, brain or skull abnormalities, tattoos on large body parts, and claustrophobia;
- 3.2.23 Pregnancy, or inability to use an effective form of contraception in women of child-bearing age;
- 3.2.24 Diabetes (Type I or Type II);
- 3.2.25 $< 5/10$ pain on average over the two-week period before the visit 2;
- 3.2.26 Lactose intolerance or sensitivity to lactose; and

3.3 Recruitment

Potential subjects will be recruited initially from a database maintained by the PI and from Northwestern's EDW. Once these sources are depleted, it is envisioned that recruitment will occur via community, online, and flyer-based methods, including ads. Potential subjects from our internal database who have provided agreement to be contacted will be called by the research staff. Those identified via EDW will be contacted once permission is granted by their physician, either by phone or by an IRB-approved mailing to be generated. Potential subjects may also be recruited online through websites including but not limited to ClinicalTrials.gov; sites for professionals who see patients with low back pain or related conditions; social media websites such as Facebook and Twitter; and/or people with low back pain or related conditions. This study will also use another online recruitment tool called Research Match, which is a secure online, national recruitment tool that is maintained by Vanderbilt University. ResearchMatch.org allows researchers to conduct feasibility or recruit potential study participants.

If potential subjects are interested in the study, they will be able to contact the research staff via the telephone number given on the website or click on a link to complete a brief online screener. To facilitate the recruitment of similar studies on low back pain conducted by [name] lab at Northwestern, participants who are screened will be asked if they are interested in learning about and participating in other studies on low back pain. If participants agree, they will be referred to and pre-screened for the other low back pain studies.

3.4 Screening

Before a person can be enrolled in the study and participate in Visit 1 (Screening Visit), s/he must first go through a maximum of two screening procedures over the phone. For potential participants who are recruited through community, online (including ClinicalTrials.gov), and flier/ad-based methods, the telephone number they contact will direct them to either NUCATS or research personnel associated with this study. NUCATS will go over a very brief pre-screening phone interview with interested individuals to verify that they are eligible to participate in the study at the most basic level (for example, verifying that they don't have any comorbid pain conditions and average pain prior to study enrollment). Those individuals who pass this pre-screening phone interview will have their contact information given to the study coordinators for a more thorough phone screening process. For these potential subjects and for individuals being recruited from the databases mentioned in 3.3, research coordinators will contact them and ask a series of more detailed questions to verify eligibility to enroll. This phone screening will go over all inclusion and exclusion criteria as indicated in the protocol, and it will also briefly explain the purpose of the study and the general outline the study. If the individual is eligible and still interested in participating at the end of this longer phone screening, the coordinator will schedule a time for them to come in for Visit 1. Additional screening procedures will happen at the first and second visits (for example, a pain rating >5/10 and discontinuation of contradictory medicines), and final eligibility will not be determined until the day before the first scan at visit 3.

4.0 TREATMENT PLAN AND STUDY INTERVENTION

4.1 Treatment Dosage and Administration

4.1.1 **Placebo Treatment:** Placebo capsules (gel caps filled with lactose NF), which will look identical to the active treatment capsules (see below), will be taken twice daily during treatment periods. During Phase 2, after a initial rating period and a 2-3 week washout of any of participant's current pain medications, participants will take placebo orally bid for 6 consecutive weeks (coming in every 3 weeks for follow-up visits and medication refills), followed by an additional 3 week washout period before study completion. One placebo

pill will be capsulated similarly to naproxen and the other will be encapsulated similarly to omeprazole.

The manufacturer for the placebo is Humco. The capsule shells (hard gelatin) will be manufactured by Capsugel (Coni Snap Size 00). Capsugel provides a certificate of analysis with each capsule batch ordered. Capsugel manufactures gelatin capsules from gelatin that complies with BSE requirements. Capsugel provides confidential detailed information about facilities, processes, articles used in manufacturing, processing, packaging, and storing of empty capsules through Type IV (Excipient) Drug Master Files submitted to the FDA. Inactive ingredients are cellulose and gelatin. Placebo capsules also contain FDC Blue #1 and FDC White.

- 4.1.2 **Active treatment:** 1 capsule of naproxen (500mg) and 1 capsule of omeprazole (20mg) will be taken orally twice daily based on the protocol for Phase 2 outlined in [3.1.1]. Each of these pills is encapsulated differently to avoid potential confusion when taking the medication. The active ingredient for the Naproxen tablets manufactured by Teva Pharmaceuticals or Amneal Pharmaceuticals, and the active ingredient for omeprazole is manufactured by Kremers. The capsule shells for both naproxen and omeprazole are manufactured by Capsugel and are the same material, size and color as those for the placebo (see 3.1.1. above).
- 4.1.3 **No-treatment:** For individuals assigned to the no treatment group, they will have the opportunity at the end of the study (when the study is un-blinded and when the efficacy results have been analyzed) to try the study medication that worked the best in alleviating back pain in the other participants, regardless of whether it was the NSAID or the placebo. If requested, this medication will be given to them at the same dosage and frequency that was used in the study, and the amount provided will last 6 weeks.
- 4.1.4 **Acquisition:** The study medications – lactose NF, Naproxen, and Omeprazole – will be purchased by the Investigational Research Pharmacy at NMH, [name]. Lactose NF will be purchased in bulk and the naproxen and omeprazole as capsules from the manufacturers noted above.
- 4.1.5 **Formulation, Packaging, and Labeling:** Over-encapsulation is conducted in the Investigational Pharmacy on a segregated and cleaned countertop. Active capsules are prepared by putting the active drug capsule inside an empty gel cap and further filling it with lactose. Placebo capsules are made by filling an empty gel cap with lactose.
- 4.1.6 **Product Storage and Stability:** Study agents will be stored at temperatures between 68-77 °F. Shelf life for Placebo and Omeprazole is 6 months; shelf life for Naproxen is 6 months. Shelf life for the rescue medication (acetaminophen) will be determined by the expiration date provided on the purchased bottles. Study medications will be stored and monitored at the Research Pharmacy; rescue medication will be stored in a designated locked filing cabinet in a locked room and will be monitored daily via temperature and accountability logs.
- 4.1.7 **Accountability Procedures:** Study product will be purchased by Northwestern Memorial Hospital Investigational Pharmacy for over-encapsulation; the rescue medication – Acetaminophen – will be bought in bulk from a nearby Walgreens pharmacy by the research staff. A defined quantity of capsules of study agent (naproxen, omeprazole, and placebo) will be supplied by NMH Investigational Pharmacy for distribution to participants. Each bottle of study agent will be filled with 52 capsules of the study agent designated by the randomization scheme – this number was calculated based on having two consecutive 3-week (21 day) treatment periods plus the additional 5 day possible visit window (26 days) multiplied by two pills a day; participants would receive a set of 2 bottles (one with 52 blue pills and another with 52 bi-colored pills) at visit 3 and another set of 2 bottles and visit 4. Regarding rescue medication, 8 pills of acetaminophen

(500mg each) will be provided at visits 1 through visit 5 by the research staff. This low number is to diminish the likelihood that participants will have a placebo response to the rescue medication and encourage them to only use the medication IF they truly need it.

Participants will be required to record all medication usage using the phone/computer app. These data are immediately logged into our server, which provides us routine overview of participants' participation and compliance, and further enhances retention of participants. If participants repeatedly miss entering these values, they are contacted by phone and instructed for compliance. A member of the research staff, unblinded monitor ([name], Back up: [name]), will contact those participants who are non-compliant with phone app ratings. Thus she will be the only staff member who will be unblinded to treatment allocation (treatment vs no treatment) Participants will be asked to return all unused study medication for each treatment visit and it will be accounted by the research pharmacy. An overall usage rate of 80% is required to be considered compliant; if a participant falls below this percentage, we will still keep them in the study but we may or may not end up using their data for future analyses. A final inventory at study conclusion will be compared with drug supplied, drug participant recorded taking, drug participants actually took, and drug returned. Returned medication will be destroyed through NMH pharmacy drug disposal services after final accountability is determined. The pharmacy will be responsible for updating and checking the study agent accountability logs. Rescue medication will only be dispensed for visits 1-5 and accountability will be determined by the research pharmacy and documented in a rescue agent accountability log. Returned medication will be destroyed through NMH pharmacy drug disposal service after final accountability is determined.

- 4.1.8 **Concomitant Medications/Treatments:** Participants must discontinue all concomitant pain medications prior to starting study treatment. Participants will be required to restrict all medications for relief of pain to only those provided during the course of this study (i.e., rescue medication, acetaminophen). Participants will be allowed to continue their existing non-pain medications as long as they are not exclusionary for study enrollment. Concomitant Medications/Treatments. Any changes in pain medication during the 30 days prior to visit 1 are not permitted, and a history of alcohol or drug abuse within the last 3 years is prohibited. Prior cannabinoid drug use is not exclusionary, but must be stopped for the duration of the study; if there is evidence that the participant is currently using cannabinoids or other recreational drugs while enrolled in the study, s/he will be dropped. Participants will be queried at each visit about other medications they are taken and any changes to this list. A cumulative log of medications will be kept in their designated study folder. Additionally, Northwestern University has an online database called eNOTIS, which is a web-based study enrollment log run by NUCATS that helps improve safety and security for participants. eNOTIS allows investigators to track participants involvement in other studies and in turn monitor if they are using other interventions from these studies at the same time. All participants are entered into eNOTIS at the beginning of the study so that we can record any of these possible interventions throughout the person's time in the study.

4.2 Duration of Therapy

Treatment may continue for **6 weeks** or until:

- Inter-current illness prevents further administration of treatment;
- Unacceptable adverse event(s);
- Patient decides to withdraw from the study; **OR**
- General or specific changes in the patient's condition render the patient unacceptable for further treatment in the judgment of the investigator.

4.3 Intervention Discontinuation: Removal of Patients from Protocol Therapy

Subjects have the right to withdraw fully or partially from the study at any time and for any reason without prejudice to his or her future medical care by the physician or at the institution. Withdrawal of full consent for a study means that the subject does not wish to receive further investigational treatment and does not wish to or is unable to continue further study participation; subject data up to withdrawal of consent will be included in the analysis of the study. Any subject may withdraw full consent to participate in the study at any time during the study. The investigator will discuss with the subject appropriate procedures for withdrawal from the study.

Withdrawal of partial consent for a study means that the subject does not wish to take protocol-required interventions any longer but is still willing to collaborate in providing further data by continuing on study (e.g., participate in all subsequent study visits or procedures). Subjects may decline to continue receiving interventions at any time during the study. If this occurs, the investigator will discuss with the subject appropriate procedures for withdrawal from protocol-required therapies (since this is placebo, there will be not withdrawal period; they can simply stop treatment). Should a subject (or a legally acceptable representative) request or decide to withdraw from the study, all efforts will be made to complete and report the observations as thoroughly as possible up to the date of withdrawal. All information should be reported on the applicable forms.

Reasons for intervention discontinuation might include:

- partial withdrawal of consent
- withdrawal of full consent
- administrative decision by the investigator
- pregnancy in a female subject (cannot be scanned)
- sudden ineligibility due to another intervention, accident, etc
- significant protocol deviation
- patient noncompliance, which may include but is not limited to:
 1. not taking the study medication (if applicable) according to the instructions given this will be monitored according to the phone/computer apps and in-person visits; if a participant has multiple indications of medication non-compliance, s/he will be disqualified and the intervention will be stopped
 2. taking non-approved concomitant medication (section 4.2)
 - a. this will be monitored according to the phone/computer apps, in-person visits, and eNOTIS
 3. not completing required study tasks, such as the daily phone/computer application
 - a. more specifically, if a participant misses 3 consecutive ratings, the research coordinator will be informed and s/he will call the person to remind them;
- AE
- other safety concerns by the investigator or NCCIH
- death
- lost to follow-up

If a patient's intervention is discontinued, the Principal Investigator will be informed, the reason for study removal will be documented, and the date the patient was removed will be listed in the Case Report Form.

4.4 Subject Retention and Ensuring an Adequate Sample Size

Although accrual will be monitored on a quarterly basis according to our DSMP, at designated time points throughout each aim of the study, we will assess whether or not we need to recruit additional participants. For Phase 2 this will be done at the half-way point and repeated for every 2 blocks until completion. At these times, if there is not a large enough drop-out rate to significantly reduce our sample size or power, we will not attempt to replace participants and continue with analysis without any replacement strategy. However, if the drop-out rate is larger than expected and lack of study retention causes us to need to increase our sample size, we will recruit additional participants and have NUCATS randomize accordingly until we have enough

participants in each group to do adequate analyses. In other words, we will continue to enroll subjects until we have an adequate number that meet our criteria, using the original randomization list. As addressed previously, we have specific procedures to help minimize subject dropout and missing data. These include the collection of detailed contact information from subjects, maintaining communications logs regarding our contacts with subjects, and a “study identity” that we will use in various communications with subjects (e.g., phone, email, letters). The computer/phone application mentioned previously will also aid us in retaining and tracking our subjects, as well as keeping up with data collection. As subjects drop out of the study, we will document reasons for dropout and address any procedural issues that may be related to dropout. At regular team meetings, we will review the number and percentage of missed assessments. Even with our data-retention plan, there will of course be missing data over time. We will compare subjects with and without missing data to determine whether any subject characteristics are systematically related to missing data. All relationships over time can be analyzed using hierarchical linear modeling (HLM), which provides maximum likelihood estimates for model parameters when data are missing at random. This model is a mixed-effects repeated measures (MMRM) analyses that includes data over time nested within participants. Participant-level variables are included in the model. For this model, participant level variables will be *Maia_Emotion*, *Erq_Suppress*, and *sign_permutation*, just as in the logistic regression model (described above). HLM allows one to model the trajectory of change within subjects, and then determine the effects of covariates (e.g., treatment group) on this trajectory. The exact model tested will be:

$$PAIN_{it} = \beta_{00} + \beta_{01} * MAIA_EMO_i + \beta_{02} * ERQ_SUPP_i + \beta_{03} * SIGN_PER_i + \beta_{10} * DAY_{it} + \beta_{11} * MAIA_EMO_i * DAY_{it} + \beta_{12} * ERQ_SUPP_i * DAY_{it} + \beta_{13} * SIGN_PER_i * DAY_{it} + r_{0i} + r_{1i} * DAY_{it} + e_{it}$$

In the equation above, $PAIN_{it}$ is the average pain rating for the t th day for the i th participant. r and e terms are error terms. Parameters will be solved for by maximum likelihood estimation. It should be noted that all aspects of this model will be inspected in Phase 2 and alternative models will be examined as needed. This includes models with more complex pain trajectories (e.g., non-linear change over time), and models with additional covariates and/or interactions among covariates

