responses are across these studies, and how they are sustained for the entire study duration. In all three studies placebo decreases pain by at least 10% within 2-4 weeks and then by an additional 10-30% within 3 months. In **figure 3** (Cox2 NSAID study), placebo treatment decreased CBP pain by >50% in approximately 35% of the group. To unequivocally state that these are placebo responses, it is necessary to have a no-treatment, observation only, control group. Nonetheless, **figure 3** strongly suggests that the placebo effect may be dichotomous, hinting at the notion of two groups: responders and non-responders—this very notion is consistent with our preliminary results. Thus, *if we can identify chronic pain patients who will respond to placebo, then we can potentially decrease the pain in this group by about 30-50%, which would be highly clinically significant.*

Figures 2 and 3 also illustrate an important property of clinical placebo, namely a sustained relief from pain for many weeks. In contrast, experimental placebo studies, by design, only examine very short duration (hours to a few days) effects. Thus, brain circuitry identified for experimental placebo is unlikely to generalize to the clinically observed placebo effects. To our knowledge, using brain circuitry to predict the placebo response in the clinical setting has not been studied outside of our lab.

The current study design specifically addresses aspects of placebo trial design that have received ethical and scientific criticism. A recent review identifies 9 distinct potential sources of bias in placebo effect studies (Hrobjartsson et al., 2011). To circumvent these problems, we rely on randomized controlled trials (RCTs) and within-subject control washout periods, perform all procedures identically across all groups, all preliminary analyses are done blinded, un-blinding occurs only after the completion of data collection, and all primary outcomes are objective brain parameters. By controlling for these factors, the natural, biologically-based propensity for some subjects to be better placebo responders than others can be objectively identified based on the proposed clinical trials.

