whether or not they took their medication. This will allow us to keep track of the stability and magnitude of pain and mood, as well as treatment compliance. To encourage them to keep up with this requirement, each time they submit these answers, they will receive 25 cents. Responses and payments will be logged automatically into a secure database that only study personnel will have access to; if participants miss more than 3 consecutive ratings in a row, research personnel will call or text them to remind them to rate or verify that their app is still working (they are automatically alerted via email by a program designed by the lab). The unblinded monitor designated for this study will check participants ratings bi-weekly to verify that ratings are being completed.

- Follow up: Patients will be asked if they wish to be added to our contact list to participate in future studies of the lab. They will also be asked if they accept to be contacted by phone 3 months and 6 months later to assess the long-term effects of the study intervention on their chronic pain intensity.

5.3 Randomization:

All randomization (and blinding, see next section) will be completed by NUCATS (see study roster in Location 2 for name of personnel). NUCATS will generate two randomization sequences, one for each group (predicted responders, Group A, and non-responders, Group B). This approach will ensure the proper 3:3:1 treatment allocation. We will use a variable block design (size of 5 and size of 10), throughout Phase 2 of the study to minimize temporal bias that can accompany longitudinal scanning studies. We don't anticipate much exclusion after randomization and enrollment based on our previous studies (although screen failures during the run-in are likely due to pain level or pathology lab results, for example). The Phase 2 overall sample size is 210 randomized 3:3:1, therefore n = 90 active treatment (n = 45 responders/non-responders), n = 90 placebo treatment (n = 45 responders/non-responders), and n = 30 no treatment (n = 15 responders/non-responders). We expect an attrition rate of ~33% for a final N = 140.

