8.0 STATISTICAL CONSIDERATIONS

8.1 Summaries of Design, Endpoints, and Analysis

8.1.1 Phase II: Study Design/Study Endpoints

Enroll and randomize 220 CBP patients into the study. Stratify into placebo responders and non-responders based on brain scan results at entry. We anticipate that about 50% of the patients will be placebo responders. All participants are randomized so that 40 receive placebo treatment, 40 active medication, and 20 no treatment. If Gender Supplement is awarded then randomization is slightly different: 60 receive placebo, 60 active medication, and 20 no treatment.

We assume that placebo responders and non-responders will show differential interaction with active medication treatment. We also expect to distinguish the four groups based on brain activity at the end of the trial, and show close correspondence between predicted and actual outcomes regarding placebo responses. Additionally, placebo non-responders should show a robust medication response, especially in comparison to the placebo non-responders receiving placebo treatment. Brain activity contrasts are done as a two-way (treatment groups) repeated measures (time: start vs. end) ANOVA (2RM-ANOVA). This is the procedure we implemented recently in a longitudinal neuroimaging study of pain chronification (Baliki et al., 2012). Post-hoc comparisons then reveal: 1) A contrast of brain activity at end of treatment between placebo non-responders with and without medication treatment to identify brain activity for bottom-up modulation of chronic pain. 2) Brain regions related to chronic pain are identified as areas commonly decreased with placebo treatment for placebo responders and medication treatment for placebo non-responders. 3) Top-down placebo and bottom-up medication effects are distinguished by identifying regions that distinctly increase in activity for placebo and medication treatments based on contrasts for the same groups. 4) The no treatment group brain activity is used as a higher-level contrast, which effectively corrects for this confound.

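### The brain contrasts rest on an unadjusted start-versus-end ANOVA of participants who have a Visit 5 scan; no section covers a missing Visit 5 scan, and the contrast is open to bias if dropout relates to the baseline scan differently by arm.

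*Combined protocol and SAP*

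**What the plan says.** - **Brain analysis.** Section 8.1.1, repeated in the Study Summary: "Brain activity contrasts are done as a two-way (treatment groups) repeated measures (time: start vs. end) ANOVA (2RM-ANOVA". Of the post-hoc comparisons in 8.1.1, contrast 1 (predicted non-responders with and without medication) is a comparison at end of treatment, not of change.
- **Scans.** Section 5.2.1 schedules them at Visit 2 (week -1) and Visit 5 (week 6) only. Equation 1 needs the Visit 2 scan, so everyone allocated through it has one.
- **Withdrawals.** Section 4.3, on withdrawal of full consent: "subject data up to withdrawal of consent will be included in the analysis of the study". It names no method. A partial withdrawer stops treatment but "is still willing to collaborate in providing further data by continuing on study (e.g., participate in all subsequent study visits or procedures".
- **Missing data.** Section 4.4: "All relationships over time can be analyzed using hierarchical linear modeling (HLM), which provides maximum likelihood estimates", under a missing-at-random assumption. The equation that follows has daily pain as outcome; the dependent variable "is the average pain rating for the t th day for the i th participant". The section also plans to compare participants with and without missing data, and to recruit more if dropout exceeds expectation.
- **Attrition.** Section 5.3: "We expect an attrition rate of ~33% for a final N = 140", from 210 randomised 3:3:1.
- **Status of the brain outcomes.** Section 1.2 states that "all primary outcomes are objective brain parameters". Section 2.3.1 gives the primary objective a pain-response endpoint.

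**The concern.** With two time points, the arm-by-time test in a repeated-measures ANOVA is a comparison of mean change among people who have both scans. The documents do not say this, but it follows from the standard method. Someone without a Visit 5 scan contributes nothing, and no section defines an imaging analysis set or says how such a person is handled.

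The change contrast among completers is unbiased if dropout is unrelated to the baseline brain measure, or related to it equally in every arm. The plan's own hypothesis gives a reason to doubt this. Equation 1 uses baseline frontal-sensorimotor connectivity to predict relief on placebo, while Figure 1 expects constant pain without treatment. If relief affects who stays (an assumption), retention depends on the baseline measure in one arm and not in another. The contrast can then show an arm difference when treatment does nothing to the brain. Stratifying by predicted class removes only part of this, because connectivity still varies within class.

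**Working it through.** **1. Attrition.** 210 x (1 - 0.33) = 140.7 and 210 x 2/3 = 140, so the stated final N reproduces. The planned loss is 70 of 210 (33.3%). If all of it came before the Visit 5 scan, complete pairs would be 60/60/20 by arm, or 30/30/10 per predicted class on a 1:1 split.

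**2. Share without a Visit 5 scan.** The 33% runs to study completion (Visit 6, week 9). If a fraction f of dropouts leave after the Visit 5 scan, the number without it is 70 x (1 - f):

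| f | Number missing | Share of 210 |
|---|---|---|
| 0 | 70 | 33% |
| 0.10 | 63 | 30% |
| 0.25 | 52.5 | 25% |
| 0.50 | 35 | 17% |

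Partial withdrawers who are still scanned lower these figures; failed scans raise them.

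**3. Where the bias comes from.** Let s be the shift in mean baseline (in SD) that dropout causes among completers in one arm relative to the other, and r the correlation between scans. With no treatment effect:
- change contrast: bias of size (1 - r) x s;
- end-of-treatment contrast: bias of size r x s, opposite in sign;
- baseline-adjusted contrast: bias zero, because adjustment removes the part carried by baseline.

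**4. Size.** Simulation with no true effect, 90 per arm, one third lost, r = 0.3 to 0.7, 4,000 replicates per setting. The dropout models and r are assumed; the documents give neither.

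| Dependence of dropout on baseline measure | Bias of change contrast (SD) | False positives, change contrast | False positives, baseline-adjusted |
|---|---|---|---|
| None, or equal in both arms | about 0 | about 5% | about 5% |
| One arm, odds ratio 1.5 per SD | 0.04-0.09 | about 6-7% | about 5% |
| One arm, odds ratio 2.7 per SD | 0.08-0.20 | 9-15% | about 5% |
| Opposite directions, odds ratio 2.7 | 0.17-0.40 | 22-47% | about 5% |

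Check against step 3: 0.20 / (1 - 0.3) = 0.29 and 0.08 / (1 - 0.7) = 0.27, so s is about 0.28 SD at both ends of the range.

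The last column holds for a two-time-point likelihood model using all baseline scans and for ANCOVA on completers only.

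**5. Smaller loss.** At odds ratio 2.7, with 25% lost, false positives are 7.6-11.8% (one arm) and 16-32% (opposite). With 17% lost they are 6.6-8.7% and 11-20%.

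**6. Within one predicted class.** At 45 per arm with dependence in one arm (odds ratio 2.7), the change contrast gives about 8-10%. Contrast 1, taken as the end-of-treatment comparison that 8.1.1 describes, gives 6-12%, rising with r.

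**7. Precision with no differential dropout.** The ratio of the ANCOVA standard error to that of the change score is the square root of (1 + r)/2. At r = 0.3 it is 0.81 and at r = 0.7 it is 0.92, so ANCOVA is about 19% to 8% more precise.

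**The case against.** The strongest reply is that the plan contains no contradiction. Section 4.3 names no method, 4.4 says only that such models can be used, and its written equation concerns daily pain. A mixed model for dense daily ratings and an ANOVA for two scans can coexist. This stands: a reader might infer that the plan commits the brain outcomes to maximum likelihood and then breaks the commitment, but no passage makes it.

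Second, discarding the baseline-only scans is not what produces the bias. ANCOVA on completers discards the same people and holds about 5%. This also stands. It moves the fault to the unadjusted contrast and leaves the finding intact.

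Third, the size depends on dropout patterns that no passage supports. At an odds ratio of 1.5 the inflation is slight, and the opposite-direction case is the extreme. That is fair, and is why the range is shown. The planned comparison of participants with and without missing data would help detect dependence, but 4.4 attaches no consequence for the imaging analysis. Recruiting replacements restores numbers without removing selection.

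Fourth, a third of participants lacking the Visit 5 scan is a tempting reading, but 33% is attrition to study end. For attrition it is an upper bound.

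Fifth, power is not the complaint. Thirty completers per treated arm and class exceed the 20 per group in 8.1.2; only no treatment by class (10) falls short.

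**Conclusion.** The point holds as a weakness of method with a gap in the plan. It is certain that the brain contrasts are specified without baseline adjustment, that the ANOVA as normally run needs both scans, and that a missing Visit 5 scan is not addressed. The size of the resulting bias is uncertain. It is nil with no or equal dependence of dropout on the baseline measure, slight at an odds ratio of 1.5 per SD in one arm, and material at 2.7 or when directions oppose. These figures rest on the assumed dropout models, correlation of 0.3-0.7 and one third lost.

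A reader might infer that the 4.4 model could simply be carried over to the scans. It could not: it has no arm term, and with two scans its random intercept, random slope and residual cannot be separated. Nor do the documents settle that the brain outcomes are primary, since Sections 1.2 and 2.3.1 differ. The change is worth making either way, because baseline adjustment also gains precision when dropout is harmless.

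**What to change.** In Section 8.1.1 and the Study Summary, make the primary brain contrast baseline-adjusted, by one of two routes:
- a two-time-point likelihood model for every randomised participant with a Visit 2 scan, with arm, predicted class, time and their interactions, an unstructured 2x2 covariance, and baseline means constrained equal across arms within class (justified by randomisation within class); or
- ANCOVA of the Visit 5 measure on the Visit 2 measure, with arm, class and arm-by-class.

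Apply the same adjustment to contrast 1. State the imaging analysis set, the handling of a missing or failed Visit 5 scan, and the missing-at-random assumption. Keep the completer ANOVA as a sensitivity analysis, which preserves comparability with Phase 1. Describe this as a new model, separate from the 4.4 equation.

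Two inconsistencies should be settled in the same edit: brain outcomes as primary (1.2) against the pain endpoint (2.3.1), and 210 randomised (5.3) against 220 (8.1.1). On 220, reaching 140 would mean a loss of 1 - 140/220 = 36.4%.

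The cost is SAP wording and longer computing for voxel-wise maps. No new data are needed.
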